9.3. Safety Analysis

Safety assessments will be made on the SAF.

9.3.1. Adverse Events

The following summaries will be provided:

- A Summary table by treatment group of the overall incidence (number and percentage) and the number of events will be provided for TEAE, TEAE related to study drug, severe TEAEs, TESAEs, TEAEs leading to study treatment discontinuation and TEAEs leading to death.

The numbers and proportions of subjects will be calculated for the following:

- TEAEs by SOC and PT
- TEAEs by SOC, PT and severity
- Severe TEAEs by SOC, PT
- Most Common ($\geq 5\%$ of patients) TEAEs by SOC and PT
- TEAEs related to study drug by SOC and PT
- TEAEs related to study drug by SOC, PT and severity
- TESAEs by SOC and PT
- TESAEs related to study drug by SOC and PT
- Severe TEAEs by SOC and PT
- Severe TEAEs related to study drug by SOC and PT
- TEAEs leading to study treatment discontinuation by SOC and PT
- Study drug-related TEAEs leading to study treatment discontinuation by SOC and PT
- TEAEs by SOC, PT and relationship to study drug
- TESAEs by SOC, PT and relationship to study drug
- TEAEs leading to death by SOC and PT

- Study drug-related TEAEs leading to death by SOC and PT

The following summaries will be provided:

- A Summary table of the overall incidence (number and percentage) will be provided for Peripheral Neuropathy Standardized MedDRA Query (SMQ) TEAEs

The numbers and proportions of subjects will be calculated for the following:

- TEAEs of Peripheral Neuropathy SMQ by SOC and PT
- TESAEs of Peripheral Neuropathy SMQ by SOC and PT
- COVID-19 TEAEs by SOC and PT

TEAEs by treatment period

The numbers and proportions of subjects with TEAEs will be summarized by treatment period and by SOC and PT. Treatment period will be categorized into grouping of:

Baseline - Day 85, Day86- Day169, Day170 -Day 253 and Day254 -.

In the analysis of TEAEs by Cycle, reoccurrences of TEAE's per subject can be shown multiple times if occurred in different cycles categories.

For each of the summaries, multiple occurrences of the same event within a subject will be counted once in the summaries by SOC and PT; multiple occurrences of the same event within a subject will be counted once in the maximum severity category (severe > moderate > mild) and/or maximum study drug relationship category (reasonable possibility / no reasonable possibility). If severity or relationship is found to be missing the most severe occurrence will be imputed for that particular summary.

Subject's data listings will be provided for: TEAEs, TESAEs, TEAE leading to discontinuation of study drug and Death

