6.1.3. Safety Analysis Set (SAF)

The SAF is defined as all randomized subjects who received at least 1 dose of study medication. Subjects will be grouped and analyzed based on the actual treatment received. Safety endpoints will be analyzed using the SAF by treatment group.

6.1.4. Exploratory biomarker Analysis Set (Ex-biomarker Set):

The Ex-biomarker Set is defined as all randomized subjects who received at least 1 dose of study medication and had any biomarker data collected after dosing. Biomarker endpoints will be analyzed using the Ex-biomarker Set

6.1.5. Exploratory Nerve conduction test Analysis Set (Ex-nerve Set):

The Ex-nerve Set is defined as all randomized subjects who received at least 1 dose of study medication and had any %CMAP, MUNIX, SNAP, and/or SNCV analysis after dosing. Nerve conduction test endpoints will be analyzed using the Ex-nerve Set.

6.1.6. Pharmacokinetic (PK) Population:

PK population includes all subjects who receive at least 1 dose of oral edaravone and who have at least 1 post-dose value for plasma concentration without important protocol deviations which may affect the PK of oral edaravone.

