6.1.7. Interim Analysis Full Analysis Set (IA)

The IA set is defined as the first 190 subjects randomized in MT-1186-A02 and who received at least 1 dose of study medication. Subjects in the IA set will be grouped and analyzed based on the planned treatment allocated (as randomized). The data provided to DMC for the futility analysis will be analyzed using the IA set.

7. STATISTICAL CONSIDERATIONS**7.1. Descriptive Statistics**

All data from all subjects randomized into the study will be included in patient data listings.

The listings will be sorted by center and subject number (and by visit, if applicable). An additional listing will be provided for screening failures.

Continuous data will be summarized descriptively using the number in the analysis set (N), the number of observations (n), mean, SD, median, minimum and maximum. Categorical data will be summarized using frequency counts and percentages. The denominator for the percentages will be the total number of subjects in the treatment group and analysis set being presented, unless otherwise specified. For visit-specific data, the number of subjects with non-missing observations at the visit in question will be used as the denominator for percent calculations. Unknown, Not Done, Not Applicable and other classifications of missing data will not be considered.

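### The TEAE-by-period table keeps departed subjects in its denominators, so late-period percentages come out too low relative to subjects at risk

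*SAP*

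**What the plan says.** SAP 9.3.1 plans this table: "The numbers and proportions of subjects with TEAEs will be summarized by treatment period", broken down by system organ class and preferred term. The periods are "Baseline - Day 85, Day86- Day169, Day170 -Day 253 and Day254", with the last left open-ended. A subject whose event recurs in different categories can be counted in more than one. No denominator is given.

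SAP 7.1 (Descriptive Statistics) gives the general rule: "The denominator for the percentages will be the total number of subjects in the treatment group and analysis set being presented, unless otherwise specified". It makes one general exception: "For visit-specific data, the number of subjects with non-missing observations at the visit in question will be used as the denominator".

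The analysis set comes from SAP 9.3: "Safety assessments will be made on the SAF". SAP 6.1.3 defines it: "The SAF is defined as all randomized subjects who received at least 1 dose of study medication".

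Protocol 15.6 has adverse events recorded until the end of safety follow-up or until the subject withdraws. SAP 4.2 assumes 30% dropout up to Week 48. SAP 8.4.1.5 and 9.1.8 compute person-years for the exposure report, but no adverse event summary in SAP 9.3.1 uses them.

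**The concern.** A subject who withdraws in the second period can add no event to the third or fourth, yet under the SAP 7.1 default still counts in both denominators. The proportions are then pulled down more in each later period, for a reason that has nothing to do with the drug.

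The SAP states no purpose for the table, but one that sets successive periods side by side will be read as a time course. The secondary objective is safety and tolerability over 48 weeks. A steady risk would look as if it were falling, and a late rise could look flat. No exposure-adjusted adverse event rate is planned that would show the reader otherwise.

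**Working it through.** **Inputs from the documents.** 190 subjects per arm and 30% dropout to Week 48 (SAP 4.2); 266 completers (SAP Appendix 1); period starts at Days 1, 86, 170 and 254 (SAP 9.3.1); Week 48 at nominal Day 337 (SAP Table 5).

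**Assumptions.** The shape of loss over time, the 20% to 40% range for total dropout, a 20% in-period risk, and every split of dropout between arms. The documents give none of these.

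**The plan's own figures.** 190 × (1 − 0.30) = 133 per arm, 266 in total, as stated. With 133 per arm, a difference of 2.6 and an SD of 7, the two-sided 5% t-test (264 df) has 85.5% power, also as stated. So the plan itself counts on losing 57 of 190 subjects per arm by Week 48.

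**Step 1: subjects remaining when each period starts.** With t days elapsed, S(t) = 0.70^(t/337) for constant-hazard loss, or 1 − 0.30 × t/337 for linear loss.

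| Period starts | Constant hazard | Linear |
|---|---|---|
| Day 1 | 190 (100%) | 190 (100%) |
| Day 86 | 174 (91.4%) | 176 (92.4%) |
| Day 170 | 159 (83.6%) | 161 (85.0%) |
| Day 254 | 145 (76.5%) | 147 (77.5%) |

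About 43 to 45 of 190 subjects per arm have left before the last period.

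**Step 2: what the table would show.** Displayed percentage = risk among those entering × S. If 29 of the 145 entering the last period have an event, the risk among them is 29/145 = 20%, but the table shows 29/190 = 15.3%. That is 1 − 0.765 = 23.5% too low in relative terms (22.5% with linear loss). A constant 20% risk among those entering would be displayed as 20.0%, 18.3%, 16.7% and 15.3% over the four periods. For the last period to show a level 20%, the risk among those entering would have to be 0.20/0.765 = 26.1%.

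**Step 3: sensitivity of the last period.**
- Total dropout 20%: S = 0.846 (constant hazard) or 0.850 (linear), so about 15% too low.
- Total dropout 40%: S = 0.681 or 0.700, so 30% to 32% too low.
- Total dropout 30%, but back-loaded (quadratic): 1 − 0.30 × (253/337)² = 0.831, so about 17% too low.

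**Step 4: comparison of arms.** Take the same true 84-day risk of 20% in both arms, constant hazards, and dropout d that continues within the period. With λ = −ln(0.80)/84 and μ = −ln(1 − d)/337, the displayed percentage is S × λ/(λ + μ) × [1 − exp(−84(λ + μ))]. Dividing by subjects entering the period removes the factor S.

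| Assumed dropout by arm | All SAF as denominator | Ratio | Entering subjects as denominator | Ratio |
|---|---|---|---|---|
| 30% and 30% | 14.7% and 14.7% | 1.00 | 19.2% and 19.2% | 1.00 |
| 25% and 35% | 15.6% and 13.8% | 0.88 | 19.3% and 19.0% | 0.98 |
| 20% and 40% | 16.5% and 12.8% | 0.78 | 19.5% and 18.8% | 0.97 |

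Ignoring dropout within the period, the 25% and 35% split gives 0.65^(253/337) / 0.75^(253/337) = 0.724/0.806 = 0.90.

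**The case against.** **The denominator is inferred.** SAP 9.3.1 does not say the table is divided by all treated subjects, the default yields to anything specified elsewhere, and visit data get an observed-subject denominator. This is right as to wording, but it leaves the rule in force. An 84-day event period is not a visit with a non-missing observation. Where the SAP wants another denominator for safety data it says so, as in 9.3.3 to 9.3.5 for laboratory, vital sign and ECG criteria. A programmer following the SAP would use the full arm.

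**Other outputs give context.** Numbness, unsteadiness and vibratory sensation are summarised by visit. Discontinuations, exposure duration and person-years are reported by arm. A careful reader could see that subjects had left and whether the arms differed. That limits the risk of being misled but does not correct the table.

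**The open last period works the other way.** For completers not entering the extension, recording runs to Week 50 (nominal Day 351), which makes 98 days against 84 or 85 in the other periods. A 20% risk per 84 days is 1 − 0.80^(98/84) = 22.9% over 98 days. If everyone entering were followed that long, the display would be 0.765 × 22.9% = 17.5%. The fall is smaller, but two unrelated errors are then mixed in one figure.

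**Post-discontinuation calls.** The calls at Weeks 24, 36 and 48 are tied in SAP 8.4.2.4 and Protocol 12.2.4 to death, tracheostomy and permanent ventilation. No rule extends TEAE recording past withdrawal.

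**The arm effect may be small.** With a true 10% rate and 25% and 35% dropout, the display is about 8.1% and 7.2%. That gap of 0.8 points compares with a standard error of about 2.7 points at 190 per arm. This objection stands.

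**Conclusion.** The point holds for the time course. The SAP's own rules put all SAF subjects of the arm under every period. With the plan's 30% dropout and constant-hazard or linear loss, the last-period percentage is about 23% too low relative to subjects at risk. The figure is 15% to 32% over the assumed 20% to 40% dropout range, and about 17% if a 30% loss is back-loaded. The 30% is a sample-size assumption, and the SAP does not say whether it includes deaths.

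Two stronger readings are tempting and are not supported.

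- A reader might infer that the table biases the comparison of regimens. It does so only if dropout differs by arm, which the documents do not state. Equal dropout gives no distortion. The ratio of 0.88 to 0.90 belongs to an assumed 25% and 35% split.
- A reader might infer that the table carries the trial's main safety question or affects the error rate. The SAP gives the table no stated purpose, test or place in the testing sequence, so type I error is untouched.

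This change should be made, but no formal conclusion of the trial depends on it.

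**What to change.** Add to SAP 9.3.1 that, for the by-period table only:

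- the denominator of each period is the number of SAF subjects in the arm still under adverse event observation at its start;
- that number appears by arm in the column header;
- exposure-adjusted incidence (subjects with an event per person-years under observation in the period) is shown for all four periods.

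The third item is needed because a start-of-period denominator does not deal with dropout within a period (the 0.97 ratio in the last row above) or with the open-ended last period. The person-years in SAP 8.4.1.5 stop at the last dose up to Week 48 and are not split by period, so observation time has to be defined to match the window in which events are counted. The same paragraph also moves from treatment period to cycle, and one term should be used.

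The cost is a few sentences and slightly more programming for one table. Data collection, blinding and the other adverse event tables are unaffected.

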9.3.1.1. Unsteadiness and Sensory Evaluation

The Unsteadiness and Sensory Evaluations will be listed and analyzed. For numbness and unsteadiness, the number and percentages of subjects with 'present' or 'absent' will be summarized by each visit up to week 48. In addition, severity will be summarized for each visit with the number and percentage of subjects in each category:

"Normal/Mild/Moderate/Severe". For this summary, the subjects with "Absent" will be classified and counted as "Normal".

A shift table to each visit up to week 48 from each baseline category will also be summarized using number and percentages.

Vibratory sensation values and change from baseline to each analysis visit window will be summarized descriptively for right and left side of the ankle.

9.3.2. Columbia Suicide Severity Rating Scale (C-SSRS)

The C-SSRS will be analyzed and listed. The frequency and percentage of subjects with each response for suicidal ideation, intensity of ideation, and suicidal behavior items will be summarized for lifetime history (screening and baseline) and the treatment period (Weeks 4, 12, 24, 48). The distribution of responses for most severe suicidal ideation and suicidal behavior will also be presented for lifetime history and the treatment period.

1. The counting method of suicidal ideation:

In each period (lifetime and treatment), the subject who has at least one of each suicidal ideation 5 items will be counted once. In case subjects will report suicidal ideation several times within a period, then the subject will be counted in the most severe suicidal ideation item.

2. The counting method of suicidal behavior:

In each period (lifetime and treatment), the subject who has at least one of each suicidal behavior 5 items and non-suicidal self-injurious behavior item will be counted once. In case subjects will report suicidal behavior with non-suicidal self-injurious behavior several times within a period, then the subject will be counted in the most severe suicidal behavior item.

3. The counting method of suicidal ideation or suicidal behavior

In each period (lifetime and treatment) the subjects who meets the criteria of (1) or (2) will be counted.

4. The counting method of non-suicidal self-injurious behavior item

In each period the subjects who has non-suicidal self-injurious behavior item will be counted.

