# 13.8 Columbia-Suicide Severity Rating Scale (C-SSRS)

The appropriately trained site personnel will attend a certified rater training for the C-SSRS, to ensure consistent and accurate ratings.

The C-SSRS is an instrument that captures the occurrence, severity, and frequency of suicide-related ideations and behaviors during the assessment period. The screening visit C-SSRS will focus on the subject's history, with emphasis on the 3 months leading up to the Screening visit, whereas subsequent assessments will compare against the last visit. The C-SSRS must be administered by appropriately trained site personnel. Suicidal ideation is classified on a 5-item scale: 1 (wish to be dead), 2 (nonspecific active suicidal thoughts), 3 (active suicidal ideation with any methods [not plan] without intent to act), 4 (active suicidal ideation with some intent to act, without specific plan), and 5 (active suicidal ideation with specific plan and intent). The C-SSRS also captures information about the intensity of ideation, specifically the frequency, duration, controllability, deterrents, and reasons for the most severe types of ideation. Suicidal behavior is classified on a 5-item scale: 0 (no suicidal behavior), 1 (preparatory acts or behavior), 2 (aborted attempt), 3 (interrupted attempt), and 4 (actual attempt). More than 1 classification can be selected provided they represent separate episodes. For actual attempts only, the actual or potential lethality is classified for the initial, most lethal, and most recent attempts. C-SSRS assessment examples are provided in Appendix 5.

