oneself. Intent does not have to be 100%. If there is any intent/desire to die associated with the act, then it can be considered as			므 므
attempt. There does not have to be any injury or harm, just the potential for injury or harm. If per son pulls trigger whi	le gun is in		
mouth but gun is droken so no injury results, this is considered an attempt.			
Inferring Intent: Even if an individual denies intent/wish to die, it may be inferred clinically from the behavior or circumstances	. For example,		
a highly lethal act that is clearly not an accident so no other intent but suicide can be inferred (e.g., gunshot to head, jumping fro	m window of a		
high floor/story). Also, if someone denies intent to die, but they thought that what they did could be lethal, intent may be inferre	:d	1	
Have you made a suicide attempt?		i i	1 1
Have you done anything to harm yourself?		Total # of	Total # of
Have you done anything dangerous where you could have died?		Attempts	Attempts
What did you do?			· I
Did you as a way to end your life?			l <del></del>
Did you want to die (even a little) when you ?			
Were you trying to end your life when you?		ł	ŀ
Or Did you think it was possible you could have died from ?			
Or did you do it purely for other reasons / without ANY intention of killing yourself (like to relieve stress,	, feel	1	
better, get sympathy, or get something else to happen)? (Self-Injurious Behavior without suicidal intent)			
If yes, describe:		Yes No	Yes No
		165 .10	
Has subject engaged in Non-Suicidal Self-Injurious Behavior?			
Interrupted Attempt:		Yes No	Yes No
When the person is interrupted (by an outside circumstance) from starting the potentially self-injurious act (if not for that, actual	l attempt would		
have occurred).			느 느
Overdose: Person has pills in hand but is stopped from ingesting. Once they ingest any pills, this becomes an attempt rather tha	n an incerrupted		
attempt. Shooting: Person has gun pointed toward self, gun is taken away by someone else, or is somehow prevented from pulli	ng trigger. Once		1
they pull the trigger, even if the gun fails to fire, it is an attempt. Jumping Person is poised to jump, is grabbed and taken down	HOM SERVE	İ	
Hanging Person has noose around neck but has not yet started to hang - is stopped from doine so.  Has there been a time when you started to do something to end your life but someone or something stopped.	ad van hafora	Total # of	Total#of
	en you begore	interrupted	interrupted.

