(1) Completely to get attention, revenge or a reaction from others (2) Mostly to get attention, revenge or a reaction from others (3) Equally to get attention, revenge or a reaction from others and to end/stop the pain	(4) Mostly to end or stop the pain (you couldn't go on living with the pain or how you were feeling)  (5) Completely to end or stop the pain (you couldn't go on living with the pain or how you were feeling)  (0) Does not apply		on 1/14/10

SUICIDAL BEHAVIOR	Since Last   Visit
(Check all that apply, so long as these are separate events; must ask about all types)	V 1511
Actual Attempt:  A potentially self-injurious act committed with at least some wish to die, as a result of act. Behavior was in part thought of as method to kill oneself. Intent	Yes No
does not have to be 100%. If there is any intent desire to die associated with the act, then it can be considered an actual suicide attempt. There does not	
have to be any injury or harm, just the potential for injury or harm. If person pulls trigger while gun is in mouth out gun is broken so no injury results,	
this is considered an attempt.  Inferring Intent: Even if an individual denies intent wish to die, it may be inferred clinically from the behavior or circumstances. For example, a highly	
lethal act that is clearly not an accident so no other intent but suicide can be inferred (e.g., grashot to bead, jumping from window of a high floor/story).	
Also, if someone denies intent to die, but they thought that what they did could be lethal, intent may be inferred.	
Have you made a suicide attempt?	
Have you done anything to harm yourself? Have you done anything dangerous where you could have died?	Total # of
What did you do?	Attempts
Did you as a way to end your life?	
Did you want to die (even a little) when you?	
Were you trying to end your life when you?	ĺ
Or did you think it was possible you could have died from ?	
Or did you do it purely for other reasons / without ANY intention of killing yourself (like to relieve stress, feel better, get	
sympathy, or get something else to happen)? (Self-Injurious Behavior without suicidal intent)  If yes, describe:	
	Yes No
Has subject engaged in Non-Suicidal Self-Injurious Behavior?	
Interrupted Attempt:  When the person is interrupted (by an outside circumstance) from starting the potentially self-injurious act (if not for that, actual attempt would have	Yes No

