8.4.3.3. Columbia Suicide Severity Rating Scale (C-SSRS)

The C-SSRS is a clinician-rated instrument that captures the occurrence, severity, and frequency of suicide-related ideations and behaviours during the assessment period.

Suicidal ideation is classified on a 5-item scale: 1 (wish to be dead), 2 (nonspecific active suicidal thoughts), 3 (active suicidal ideation with any methods [not plan] without intent to act), 4 (active suicidal ideation with some intent to act, without specific plan), and 5 (active suicidal ideation with specific plan and intent). The C-SSRS also captures information about the intensity of ideation, specifically the frequency, duration, controllability, deterrents, and reasons for the most severe types of ideation. Suicidal behavior is classified on a 5-item scale: 0 (no suicidal behavior), 1 (preparatory acts or behavior), 2 (aborted attempt), 3 (interrupted attempt), and 4 (actual attempt). More than 1 classification can be selected provided they represent separate episodes. For actual attempts only, the actual or potential lethality is classified for the initial, most lethal, and most recent attempts. C-SSRS will be evaluated at screening, baseline, Week 4, Week 12, Week 24, and Week 48.

The sever level of suicidal ideation 5 items from low to high:

- 1: Wish to be dead
- 2: Non-specific active suicidal thoughts
- 3: Active suicidal ideation with any methods (not plan) without intent to act
- 4: Active suicidal ideation with some intent to act, without specific plan
- 5: Active suicidal ideation with specific plan and intent

The sever level of suicidal behavior 5 items from low to high:

- 1: Preparatory Acts or Behavior
- 2: Aborted Attempt
- 3: Interrupted Attempt
- 4: Actual Attempt
- 5: Suicidal Behavior

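### SAP 9.3.2 puts non-suicidal self-injury into the criterion for suicidal behaviour, so a subject with only that item is counted as having suicidal behaviour

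*SAP*

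**What the plan says.** SAP 9.3.2 sets out four counting methods, for the lifetime and treatment periods.

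- Method 1 counts suicidal ideation.
- Method 2 counts suicidal behaviour: "the subject who has at least one of each suicidal behavior 5 items and non-suicidal self-injurious behavior item will be counted once". Its second sentence deals with subjects who report suicidal behaviour together with non-suicidal self-injury: "then the subject will be counted in the most severe suicidal behavior item".
- Method 3 is the combined count of ideation or behaviour: "the subjects who meets the criteria of (1) or (2) will be counted".
- Method 4 counts the self-injury item separately: "In each period the subjects who has non-suicidal self-injurious behavior item will be counted".

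Three other places define the items.

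- Protocol 13.8: "Suicidal behavior is classified on a 5-item scale: 0 (no suicidal behavior), 1 (preparatory acts or behavior" and so on up to 4, actual attempt. There is no self-injury category.
- SAP 8.4.3.3 repeats that 0 to 4 scale in prose. It then gives a ranked list ("The sever level of suicidal behavior 5 items from low to high"): preparatory acts, aborted attempt, interrupted attempt, actual attempt and, at level 5, an item called Suicidal Behavior. Non-suicidal self-injury is not in the list.
- The C-SSRS form in Protocol Appendix 5 describes the item as "Self-Injurious Behavior without suicidal intent" and gives it its own yes/no question: "Has subject engaged in Non-Suicidal Self-Injurious Behavior".

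Protocol 17.4.5.9 plans a table, by treatment group, of subjects with suicidal ideation or suicidal behaviour. It does not mention non-suicidal self-injury.

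**The concern.** Method 2 decides who is reported as having suicidal behaviour, and method 3 takes that decision into the combined table. If the criterion admits an item that the form defines by the absence of suicidal intent, a subject can be reported under the wrong safety heading.

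The C-SSRS is a listed safety endpoint in both documents. SAP section 2 says that analysis details in the SAP take precedence over those in the protocol, so the method 2 wording governs over Protocol 17.4.5.9. SAP section 11, which lists changes from the protocol, does not mention this one.

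**Working it through.** There is no plan figure to reproduce. The check is to take every combination of ideation (I), suicidal behaviour (B) and non-suicidal self-injury (N), apply methods 2 and 3, and compare the result with the classification in Protocol 13.8, SAP 8.4.3.3 and the form. The targets are B for method 2, and I or B for method 3.

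Method 2 is read in two ways: inclusively (B or N) and conjunctively (B and N). Method 3 is I or method 2. An asterisk marks a result that differs from its target.

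| I | B | N | Target B | M2 inclusive | M2 conjunctive | Target I or B | M3 inclusive | M3 conjunctive |
|---|---|---|---|---|---|---|---|---|
| 0 | 0 | 0 | 0 | 0 | 0 | 0 | 0 | 0 |
| 0 | 0 | 1 | 0 | 1* | 0 | 0 | 1* | 0 |
| 0 | 1 | 0 | 1 | 1 | 0* | 1 | 1 | 0* |
| 0 | 1 | 1 | 1 | 1 | 1 | 1 | 1 | 1 |
| 1 | 0 | 0 | 0 | 0 | 0 | 1 | 1 | 1 |
| 1 | 0 | 1 | 0 | 1* | 0 | 1 | 1 | 1 |
| 1 | 1 | 0 | 1 | 1 | 0* | 1 | 1 | 1 |
| 1 | 1 | 1 | 1 | 1 | 1 | 1 | 1 | 1 |

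- **Inclusive.** Method 2 wrongly counts 2 of 8 profiles, those with self-injury and no suicidal behaviour. Method 3 wrongly counts 1 of 8, self-injury with neither ideation nor behaviour.
- **Conjunctive.** Method 2 wrongly omits 2 of 8 profiles, those with suicidal behaviour and no self-injury. Method 3 wrongly omits 1 of 8.
- **Method 2 restricted to the suicidal-behaviour items.** 0 of 8 are wrong in method 2 and 0 of 8 in method 3.

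**Placement.** The second sentence of method 2 assigns a level only when suicidal behaviour and self-injury are both reported. A subject with N = 1 and B = 0 is in the total but has no level in the SAP 8.4.3.3 list, so the total and the severity distribution could disagree.

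**Size.** The planned arm is 190 subjects (Protocol 9.1). The number k of subjects with self-injury and no suicidal behaviour is not in the documents, so a range is assumed. The shift in an arm's percentage is 100 × k / 190:

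- k = 0: 0
- k = 1: 0.53 points
- k = 2: 1.05 points
- k = 4: 2.11 points

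For method 3, only those of the k subjects who also have no ideation count.

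**The case against.** The strongest reply is that this is loose drafting. Method 2 could be a rule for table rows: each of the five items, and the self-injury item as a sixth row, is counted once per subject. The self-injury question does sit in the suicidal-behaviour section of the form, so showing it in that table is understandable. The second sentence also gives suicidal behaviour precedence when both are reported.

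That reading would settle the matter if method 2 stood alone. Method 3, however, uses method 2 as a criterion that a subject meets or does not meet, and that criterion names the self-injury item. A programmer following the text would include it.

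Several parts of the reply do stand:

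- SAP 9.3.2 also summarises each behaviour item, method 4 shows self-injury by itself, and the C-SSRS data are listed. A careful reader could recover the right classification.
- The conjunctive reading is weak. Taken that literally, the sentence would also require all five behaviours, which cannot be meant. A reader might infer that subjects with an actual attempt will drop out of the count; the text does not support that as the likely outcome.
- A reader might also infer that the suicidal-behaviour tables are wrong throughout, or inflated by a large relative amount. The documents support neither. The inclusive error needs a subject with self-injury and no suicidal behaviour, and a relative figure needs a count of true cases, which is not given. Nor can Protocol exclusion 8 be used to argue that counts will be small in both periods: it covers only the 3 months before screening, so it does not limit the lifetime counts.

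**Conclusion.** The point holds in a limited form. Method 2 includes an item that the protocol, the SAP's own severity list and the form all keep outside suicidal behaviour. On the natural inclusive reading it misclassifies subjects with non-suicidal self-injury and no suicidal behaviour. The combined count is affected only for those who also have no ideation.

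Each affected subject shifts an arm of 190 by about 0.5 percentage points. If there are none, the counts are unchanged. No hypothesis test, alpha, futility rule or efficacy result depends on these tables. The conclusion rests on reading the list in method 2 inclusively and on method 3 applying method 2 at subject level, as it is written.

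**What to change.** Before database lock, reword method 2 along these lines: *In each period, a subject with at least one of the suicidal behavior items is counted once; if several are reported within the period, the subject is counted in the most severe item.* This removes both mentions of non-suicidal self-injury. It also removes the phrase requiring at least one of each, which would remain a problem if only the self-injury words were deleted. Keep self-injury in method 4. Method 3 then needs no change.

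In the same edit, reconcile the ranking in SAP 8.4.3.3 with Protocol 13.8. The SAP list puts the summary item Suicidal Behavior at level 5, above actual attempt at level 4. In Protocol 13.8, and in the SAP's own prose, actual attempt is the highest level. On the form the summary item is a yes/no question on whether any suicidal behaviour was present. If it is ranked highest, any subject with that box ticked could be placed at level 5, and the severity distribution would say little.

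The cost is a short rewording of method 2, a correction to one list and the matching programming conditions. No new data are needed.
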